Each individual patient should only be included in EAGLE once. Following the index procedure that is included in EAGLE 2, patients undergoing additional procedures within the study window should not be included for a second time.

Patient identification

Each participating country and hospital will decide how best to identify eligible patients.

Patients can be identified either before, during, or after surgery. As guidance, it is anticipated that patients may be identified from any of the following settings, but that this should preferentially be performed pre-operatively:

- Pre-operatively: surgical outpatient clinics (e.g. when the patient is being booked for elective surgery); planned theatre lists (e.g. at the time of admission for surgery); emergency surgical admissions (e.g. at the time that a decision to operate is made)
- Intra-operatively: by the operating surgical teams during the in-theatre Safe-anastomosis checklist, once the procedure eligibility has been confirmed.
- Post-operatively but before discharge: by either the operating surgeon or by review from the research team.

Patients will be identified by a suitable healthcare staff who may include:

- The senior operating surgeon
- Any doctor involved in the patients' care (e.g. surgeon in training)
- Research nurse
- Research secretary

Patient Consent

This is a quality control audit. We anticipate therefore that most ethics review boards will waive the requirement for patient consent, as only pseudoanonymised audit data will be collected. However, there may be variation in international regulations and it will be the responsibility of the local project lead to seek local research ethics committee advice in each participating country to determine whether informed consent should be sought.

DATA COLLECTION

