Data management and data security within BiCOPS will abide by the requirements of the General Data Protection Regulations (GDPR) and any subsequent amendments. The audit will be conducted at collaborating sites in accordance with the country-specific data protection requirements.

Access to data will be restricted by usernames and passwords, at participating sites. Each participant will be allocated a unique study number at entry. All communication will use this as the identifier. All data will be analysed and reported in summary format. No individual patient will be identifiable.

Confidentiality and data protection

Any correspondence between the EAGLE 2 study office and hospital sites will use the anonymous ID code only.

The linkage between the study ID code and participants will be maintained in strict confidence at participating sites. This data will not be submitted to the EAGLE 2 study office and will not be sent outside of the participating site.

Confidentiality of all participant's data will be maintained and there will be no disclosure of information by which participants may be identified to any third party other than those directly involved in the treatment of the participant.

Data is owned by the ESCP and can be used for future research without renewed permissions from the participants centres. However, any publication based on the collected data will include the collaborating participants as co-authors (see below please).

Access to final dataset

The ESCP Cohort Studies Working Group welcomes the use of the data for further research that benefits patients. Requests can be submitted to the ESCP Cohort Studies Working Group. Data Sharing is subject to ESCP approval and the appropriate safeguarding as determined by the ESCP. Any future subprojects should also comply with our policy of a single corporate authorship e.g. "European Society of Coloproctology (ESCP) collaborating group. However, authors'

contributions will be highlighted in accordance with the recommendations for the conduct, reporting, editing, and publication of scholarly work in medical journals (commonly referred to as the Vancouver Convention) by the International Committee of Medical Journal Editors (ICMJE).

Timeline and schedule of events

| | | Baseline data | After Surgery | 30-day follow-up |
|---|--|---------------|---------------|------------------|
| Clinician reported audit - all patients | Patient information | ✓ | | |
| | Surgery information | | ✓ | |

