| | Short-term Complications / reinterventions | | | ✓ |

Training platform

The training platform for the audit is the ESCP Safe-anastomosis Online Educational Module. This is an Electronic Learning Management System which houses a five-modular educational platform, freely accessible at <https://eagle-escp.eu.com/>. The modules are:

1. **Decision making**, including a pre-operative risk stratification tool for anastomotic leak
2. **ESCP Safe-anastomosis checklist**, including components and implementation within a theatre team
3. **Preparing for anastomosis**, including anastomotic healing bowel preparation, choice of stapled versus handsewn anastomoses
4. **Stapled anastomosis**, including harmonising technique and checking for technical failure.
5. **Handsewn anastomosis**, including harmonising technique, common variations and checking for technical failure.

It is intended that this educational module should be completed by any providers of colorectal surgical procedures (including consultant/attending surgeons, trainee/resident surgeons, and surgical care practitioners/allied healthcare professionals in surgery) prior to participation in the audit.

Validation of learning platform

The training program has been reviewed by the ESCP Education Committee and revised. It has also been reviewed by the independent Study Steering Committee. More than 2500 surgeons completed the online training during delivery of the EAGLE 1 study.

Data collection and follow-up

Data will be collected in two phases. During the index admission pre-operative and intra-operative data will be collected. Local Principal Investigators will establish pathways in their hospitals to ensure robust data collection; for example, pre-operative data could be collected on the morning prior to surgery, with intra-operative data fields completed in theatre immediately following completion of the procedure. Alternatively, all data could be collected in theatre, or in the post-operative ward.

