All patients, including those who did not have a primary anastomosis, will be followed-up to a maximum of 30-days post-operatively (with Day 0 being the day of surgery) by a review of their inpatient health records, routine clinic visit letters, and reports for post-operative radiological investigations arranged as part of normal patient care. There will be no additional patient contact (telephone or in-person) beyond what is normal clinical practice at each centre. The study is designed efficiently so that existing patient follow-up pathways and health records can be used, with only data that is routinely collected as part of normal clinical care being captured.

Most anastomotic leaks following ileocolic anastomosis occur in the early post-operative period (days 4-14). Although a small number of anastomotic leaks occur beyond day 30, limiting follow-up to 30 days will ensure that the vast majority of leaks are captured.

Statistical analysis plan

This will be conducted on an intention-to-treat basis i.e. all patients recorded in the database during the scheduled 2-month recruitment periods will be included, and those in the second period will be considered exposed to the intervention regardless of whether learning from the intervention was actually implemented. The primary outcome will be 30-day anastomotic leak rate. In the primary analysis, 30-day leak rate will be modelled using mixed effects logistic regression with random cluster (hospital) effects allowing inclusion of baseline risk factors such as co-morbid disease and ASA score and adjustment for a fixed time effect between time periods.

Sample size

Based on feasibility (below), we assume that if each hospital provides data on 10 patients over a 2-month recruitment period (5 per hospital per month) then adequate sample size will be obtained to allow statistical analysis (see below please).

Projected recruitment

Data for 3,208 right colectomies was submitted by 284 centres over a 2 month period to the 2015 ESCP Right Hemicolectomy Audit; an average of 11.3 patients per 2 months. 81% the sites recruited >10 patients over the 2-month period. A mean of 10 patients per centre is required for each 2 month recruitment period.

| Patients per centre (2 months) | Proportion of centres |
|---------------------------------------|------------------------------|
| 1-5 | 19% (n=53) |
| 6-10 | 37% (n=104) |
| 11-15 | 22% (n=63) |
| 16-20 | 14% (n=39) |
| 21-30 | 6% (n=17) |
| 31+ | 3% (n=8) |

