APPENDIX 1. EAGLE 2 Case Report Form

| Local Patient Identifier | not uploaded to REDCap | Unique REDCap Identifier | |
|---|---|--------------------------|--|
| Pre-operative data | | | |
| Age (on day of operation) | Years | | |
| Sex | Male / Female | | |
| American Society of Anaesthesiologists (ASA) grade | 1 / 2 / 3/ 4/ 5 | | |
| Previous abdominal surgery | No / Yes | | |
| History of ischemic heart disease or cerebrovascular disease | No / Yes | | |
| History of diabetes mellitus | No / Yes | | |
| Body Mass Index >30 | No / Yes | | |
| Oral anti-coagulants | No / Yes | | |
| Pre-operative total protein level (g/dL) – nearest 0.5 units | | | |
| Pre-operative haemoglobin (g/dL) | | | |
| Procedure indication | Malignancy / Inflammatory bowel disease / Other | | |
| Intra-operative data | | | |
| Bowel preparation | None / Mechanical bowel preparation only / Mechanical bowel preparation with oral antibiotics | | |
| Primary operating surgeon | Consultant colorectal surgeon / Trainee colorectal surgeon / Consultant general surgeon / Trainee general surgeon | | |
| Most senior surgeon in theatre | Consultant colorectal surgeon / Trainee colorectal surgeon / Consultant general surgeon / Trainee general surgeon | | |
| Procedure urgency | Elective (planned) / Expedited (within two weeks of decision to operate) / Emergency (unplanned) | | |
| Operative approach | Open, Laparoscopic (completion, conversion to open), Robotic (completion, conversion to open) | | |
| Operative field contamination | Clean-contaminated / Contaminated / Dirty | | |
| Anastomosis formed | Stapled / Handsewn / No anastomosis (end ileostomy formation) | | |
| If yes: Anastomotic configuration | Side-to-side / end-to-side / end-to-end | | |
| If yes: Is there a defunctioning loop ileostomy | No / Yes | | |

| | |
|---|--|
| If yes: Was the anastomosis tested? | No / Yes -air leak test / Yes - probed with forceps |
| If yes: Did the anastomosis require revision? | No / Yes |
| Intra-operative complications | Blood loss >1L / Operating time >4h / Solid organ or ureteric injury / Vascular injury / Blood transfusion / Hemodynamic instability / Vasopressor requirement (select all that apply) |
| Duration of surgery (minutes) knife-to-skin to completion of skin closure | 1-60 / 61-119/ 120-179/ 180-239/ ≥240 |
| Was an ESCP Safe-anastomosis Checklist completed? | Yes / No |
| Was anastomotic leak risk calculated pre-operatively ? | Yes / No |

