| Was anastomotic leak risk calculated intra-operatively ? | Yes / No |
| Has the senior surgeon completed the Safe-anastomosis module? | Yes / No |
| Post-operative data | |
| Post-operative critical care admission | None / Planned from theatre / Unplanned from theatre / Unplanned from ward |
| Total length of hospital stay | Days (up to 30 post-operative days) |
| Anastomotic leak or intra-abdominal/pelvic collection | None / Grade A – requiring no further intervention, radiologically diagnosed / Grade B – requiring radiological reintervention / Grade C – requiring surgical reintervention |
| If yes: How was the leak diagnosed? | Clinical diagnosis only/ Ultrasound imaging/ CT imaging/ MR imaging/ Intra-operative diagnosis |
| Re-operation within 30 days | No / Yes |
| Re-admission within 30 days | No / Yes |
| Mortality within 30 days | No / Yes |

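### The senior-surgeon training item is undated, and pre- and intra-operative items may be recorded on the ward with no field showing whether they preceded the leak

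*Protocol*

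**What the plan says.** **Timing of recording.** Protocol, Data collection and follow-up, sets one window: "During the index admission pre-operative and intra-operative data will be collected". Collection on the morning of surgery and in theatre is offered as an example only, and is followed by "Alternatively, all data could be collected in theatre, or in the post-operative ward". The Timeline and schedule of events is tighter: it ticks "Patient information" under baseline and surgery information under the after-surgery column. Patient identification prefers the pre-operative route but also permits "Post-operatively but before discharge: by either the operating surgeon or by review from the research team".

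**Timing of the outcome.** Data collection and follow-up also states: "Most anastomotic leaks following ileocolic anastomosis occur in the early post-operative period (days 4-14").

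**Items on the form.** Appendix 1 lists, before the post-operative block, "Was an ESCP Safe-anastomosis Checklist completed", "Was anastomotic leak risk calculated pre-operatively", the matching intra-operative risk question, and "Has the senior surgeon completed the Safe-anastomosis module? | Yes / No". All are undated yes/no fields.

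**What training is meant to signify.** Training platform intends the module to be finished before a provider takes part in the audit. Planned additional analyses groups hospitals by the proportion of operating surgeons trained before data collection (80% or more, 50-79%, under 50%). Uptake of the platform is also a secondary objective.

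**The concern.** There are two linked weaknesses.

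First, the training item asks about status at the moment the form is completed, while the protocol's own definitions refer to status before participation or before data collection. The item as worded cannot establish either.

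Second, a form completed on the ward may be completed after a leak is known. Some answers are then open to hindsight, and nothing on the form lets an analyst see which ones.

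At stake is how far the audit's record of implementation can be trusted: who was trained, whether the checklist was used and whether leak risk was calculated. The audit is meant to validate an earlier result that includes a fall of almost 50% in centres with 80% of surgeons trained, so a training status that cannot be placed in time weakens any reading of that gradient.

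**Working it through.** The protocol states no figure on this point, so there is none to reproduce. The check sets the sections side by side.

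**1. Do the recording window and the leak window overlap?** Recording is bounded only by the index admission, and most leaks are placed at days 4 to 14. They overlap for any patient still in hospital on day 4 or later whose form is not yet complete. The protocol gives no length-of-stay figure and no share of late forms, so the overlap is possible but its frequency is unknown.

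**2. Could an analyst detect it?** Appendix 1 lists no operation date, form-completion day, leak date or training date. Data Management allows a paper form to be transferred to the database later, so the time of database entry would not show when the answer was given.

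**3. What does the training item record?** Let O be the time of operation, T the time training was completed and F the time the form was completed.
- Status intended: trained if T is before O.
- Status recorded: trained if T is before F.
- The two differ exactly when T falls between O and F.

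This error runs one way only: an untrained operation is recorded as trained. By this route uptake can only be overstated. If F tends to be later for leak patients, more of their operations are moved into the trained group, and training looks worse than it was. Hindsight that turns a yes into a no for leak cases works the other way. The net direction is therefore not fixed.

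**4. Could it move a hospital between training groups?** Only if the proportion is taken from this item, which the protocol does not say. If it were, misdating one of n operating surgeons raises the hospital's proportion by 1/n. That carries it into the top group whenever its true proportion is below 80% by no more than 1/n.

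**5. Which items are exposed?**

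| Item | Independent check described in the protocol | Exposure to late recording |
|---|---|---|
| Age, laboratory values, usually ASA grade | Medical notes | Small |
| Field contamination | Notes, but a judgement | Some |
| Checklist used, risk calculated | No specific record described | Main |
| Senior surgeon trained | Notes not shown to hold it | Main |

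**6. A purely hypothetical scale.** Suppose checklist use has no true effect and a share of leak cases have yes changed to no.
- 50% use, 10% changed: 0.50 × 0.90 = 0.45; odds ratio (0.45/0.55)/(0.50/0.50) = 0.82.
- 50% use, 5% changed: 0.475/0.525 = 0.90.
- 80% use, 10% changed: 0.80 × 0.90 = 0.72; (0.72/0.28)/(0.80/0.20) = 0.64.
- 80% use, 5% changed: (0.76/0.24)/(0.80/0.20) = 0.79.
- Reverse change (no to yes) at 10%: (0.55/0.45)/1 = 1.22 at 50% use; (0.82/0.18)/4 = 1.14 at 80% use.

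Only forms completed after diagnosis can be altered in this way. If 20% were late, half of those would have to be changed to reach 10% overall (0.20 × 0.50 = 0.10). Every rate here is assumed, and the protocol plans no checklist analysis. The figures show that such an association would be sensitive to recording, not that one will be distorted.

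**The case against.** The strongest reply is that no planned analysis is shown to suffer. The Statistical analysis plan section assigns exposure by period, whether or not the training was applied in practice. The patient-level subgroups do not include checklist use, risk calculation or senior-surgeon training. The hospital-level training subgroup carries its own time anchor, and its proportion could come from the learning management system rather than the form. The named adjusters, co-morbidity and ASA, come from routine notes, and a value copied late is not a value assessed late. Local leads must set up robust collection pathways, and pre-operative identification is preferred.

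Most of that stands, and it rules out several stronger readings:
- A reader might infer that the primary exposure or the primary risk adjustment is biased. The period rule excludes the first. Source data in the notes leave little of the second.
- A reader might infer that leak patients are the ones still on the ward at days 4 to 14. No length-of-stay figure supports this.
- A reader might take the checklist and training items as the only patient-level trace of the intervention. The form also records bowel preparation, anastomotic technique, configuration and testing, which overlap the module content.
- A reader might take an odds ratio of 0.82 as a forecast. It rests on assumed rates for an analysis that is not planned.

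What the reply does not remove is narrower. The training item cannot show prior completion, nothing in the protocol says the notes hold it, and late entries cannot be identified from the listed fields.

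**Conclusion.** The point holds as a limited data-quality defect. The training item does not measure status at the operation. In addition, recording on the ward is allowed without a limit short of discharge and without a field that would reveal entries made after a leak. The effect falls mainly on the training, checklist, risk-calculation and contamination items, and on any uptake or training proportion derived from them. It does not alter primary-analysis exposure and matters little for items that can be verified in the notes.

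The size cannot be derived from the protocol. It depends on the share of forms completed late, the share of surgeons trained between operation and form entry, and whether the training proportion uses this item, none of which is stated. That recording may happen at any time in the admission is an inference from the missing limit, not the protocol's wording. Late recording is permitted, not required. This is a worthwhile, low-cost improvement, not a threat to the main result.

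**What to change.** 1. Reword the training item to: *Had the senior surgeon completed the modules before the date of this operation?* Alternatively, take completion dates from the learning platform. State which source supplies the hospital-level training proportion.
2. Add one field for the post-operative day on which the pre- and intra-operative section was completed, on paper or in the database. Set a single target of no later than day 3, which precedes the protocol's stated leak window. A day number is enough; no calendar date is needed.
3. Keep the ward option and post-operative identification, so that consecutive inclusion is preserved. Align the schedule table and the text of Data collection and follow-up with the same target.
4. Flag forms completed after day 3, keep those patients in the audit, and repeat without them any analysis that uses the training or checklist items.

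The cost is one extra field, one reworded item and a sentence of text. The downside is that some late-identified patients will be flagged. Patient care does not change.

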Background: Anastomotic leak (Al) is a severe, potentially life-threatening complication following right colectomy. Internationally, anastomotic leak occurs after 8% of right colectomies. Prospective cohort data demonstrate that patient selection, intra-operative factors, and technical variation are risk factors for anastomotic leak. The EAGLE study investigated an educational platform to reduce Al. It showed an absolute reduction in leaks of 20% following implementation and found that in centres where 80% of surgeons undertook the training, the anastomotic leak rate fell by almost 50%. EAGLE 2 is a snapshot audit of centres undertaking the educational intervention to validate the findings from the randomised trial.

Aim: To measure the anastomotic leak rate following right sided large bowel anastomosis in centres where the surgical teams have undertaken the EAGLE platform training.

Design: Prospective audit with clinician derived baseline clinical data and short-term 30-day outcomes for patients undergoing right colectomy and ileocecal resection.

Eligibility: Any hospital or surgical unit performing elective and/or emergency colorectal surgery. Adults (age 18 years and above) undergoing right colectomy or ileocaecal resection for any indication are eligible, including elective, expedited or emergency surgery by open, laparoscopic or robotic approaches.

Primary Outcome measure: 30-day anastomotic leak rate, defined as clinical or radiologically detected anastomotic leak or intra-abdominal or pelvic collection.

Sample size: a consecutive series of cases, collected over an 8 week period, of patients undergoing right sided large bowel anastomosis. The study is open to any centres where the surgical team have undertaken the educational training. These may be centres from EAGLE 1 or new centres that did not take part in EAGLE 1.

BACKGROUND

Clinical problem

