Anastomotic leak has been recognised as a priority research topic by the James Lind Alliance. A comprehensive systematic review and meta-analysis of leak prevention strategies in right colectomy demonstrated a low-quality evidence base to support specific technical and perioperative interventions. Most evidence was based on single-centre observational studies at high-risk of bias. Where randomised studies have been conducted, their interpretation is limited by explanatory designs under-powering, or a lack of contemporary data. International, pragmatic studies are required to improve the evidence base for anastomosis formation, and benefit patients undergoing right colectomy. The 2019 ESCP Hamburg Declaration emphasized the critical importance of addressing unacceptable variation in anastomotic leak rates by quality improvement. The EAGLE 2 audit aims to capture evidence for the beneficial effect of completion of the EAGLE online training to address this variation.

Justification of patient population

Right colectomy is the most commonly performed large bowel resection in the world. It is performed for both acute and chronic conditions, across high, middle and low-income settings. Despite the high risk of anastomotic leak demonstrated in ESCP audits, right colectomy is often considered a simpler and lower-risk operation than left colectomy or rectal surgery, and consequently consultants may not always be the lead surgeon; in selected cases trainees may perform this operation independently. Finally, it is performed by specialist colorectal surgeons and general surgeons.

Rationale for study design

The prospective audit will result in the generation of a large, international dataset of real-world data on the impact of completion of the EAGLE training modules on anastomotic leak rate in centres where most surgeons complete the training.

AIMS & OBJECTIVES

Primary objective

- To measure the anastomotic leak rate following right sided large bowel anastomosis in centres where the surgical teams have undertaken the EAGLE platform training.

Secondary clinical objectives

- To assess the uptake and acceptability of the online training platform.

Primary outcome measure

The primary outcome measure is anastomotic leak within 30-days of surgery (with Day 0 as the day of surgery). The denominator for the primary outcome is the total for patients who had a primary anastomosis. The numerator is anastomotic leak, defined as a composite of either:

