- Anastomotic leakage identified radiologically or clinically
or
- Intraperitoneal (abdominal or pelvic) fluid collection identified radiologically, as per the Centre for Disease Control Criteria for Organ Space infection
or
- Entero-enteric fistula identified radiologically

Secondary outcome measures

- The denominator is the total for patients who had a primary anastomosis:
- Reoperation for anastomotic leak, within 30-days
- The denominator is the total for all patients:
- Reoperation for any cause, within 30-days
- Unplanned admission to critical care, within 30 days
- Readmission within 30 days.
- Post-operative length of hospital stay, up to 30-days
- Mortality within 30-days.
- Rate of ileostomy without anastomosis.
- Rate of defunctioning ileostomy with anastomosis.

Study Design

International prospective audit.

ELIGIBILITY

Hospital inclusion criteria

Any hospital or surgical unit performing elective and/or emergency colorectal surgery. There are no restrictions for hospital/unit size or case volume. Participation in EAGLE 1 is not a pre-requisite.

Participating sites will be expected to recruit all eligible patients within a consecutive 8-week period.

At hospital level, data completeness of 95% will be required to be part of this audit.

Patient inclusion criteria

All adult patients (age 18 years and above) undergoing right colectomy with or without primary anastomosis. Right colectomy is defined as ileocaecal resection or right hemicolectomy (any colonic transection with the distal resection margin proximal to the splenic flexure).

All patients undergoing right colectomy are eligible, including those who do not have an anastomosis and are defunctioned by a proximal stoma.

Procedures for any pathology, via any operative approach (open, laparoscopic, robotic or converted) are eligible.

Elective (surgery on a planned admission), expedited (within 48 hours), and emergency (surgery on an unplanned admission) procedures are eligible.

Patient exclusion criteria

Patients undergoing more than one gastrointestinal anastomosis during the same operation.

In Crohn's disease, additional upstream strictureoplasty or resection/anastomosis to treat disease or strictures at the same operation.

Simultaneous right colectomy and hyperthermic intraperitoneal chemotherapy (HIPEC) and/or cytoreductive surgery.

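### The primary analysis is written for two recruitment periods, but the audit as described has one, so the period-based exposure and time effect cannot be estimated

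*Protocol*

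**What the plan says.** **Design.** The synopsis (Background) states that "EAGLE 2 is a snapshot audit of centres undertaking the educational intervention to validate the findings from the randomised trial". Its sample-size entry describes "a consecutive series of cases, collected over an 8 week period, of patients undergoing right sided large bowel anastomosis", and adds: "The study is open to any centres where the surgical team have undertaken the educational training". Under Hospital inclusion criteria: "Participating sites will be expected to recruit all eligible patients within a consecutive 8-week period". The Training platform section intends the module to be completed "prior to participation in the audit".

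**Objective.** The primary objective is "To measure the anastomotic leak rate following right sided large bowel anastomosis in centres where the surgical teams have undertaken the EAGLE platform training". The primary outcome is a proportion: leaks within 30 days over patients who had a primary anastomosis.

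**Analysis.** The Statistical analysis plan section of the protocol calls the analysis intention-to-treat, refers to 2-month recruitment periods in the plural, and says that "those in the second period will be considered exposed to the intervention regardless of whether learning from the intervention was actually implemented". The primary model is a mixed effects logistic regression with random hospital effects, baseline risk factors and "adjustment for a fixed time effect between time periods".

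**Further analyses.** Planned additional analyses groups centres by training uptake before a post-implementation phase of data collection. It also plans a reverse analysis that contrasts hospitals whose results changed a great deal with those whose results did not.

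**The concern.** The design sections and the analysis section describe different studies. The design is a single snapshot in centres that are meant to be trained already. The analysis assumes an earlier period without the intervention, a later period with it, and a time effect separating the two. Nothing in the protocol defines the earlier period.

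This is a fault in a rule that the protocol fixes for its primary analysis, so it differs from a detail left to a separate SAP. An analyst who follows the text reaches a term that cannot be fitted and must change the primary model, possibly after seeing the data. The estimate that the objective asks for, one leak rate with its uncertainty, is not specified. The intention-to-treat label and the exposure rule may also lead readers to expect a before/after effect of training, which this audit does not measure.

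**Working it through.** **1. Periods and exposure, section by section**

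| Place in protocol | What it implies |
|---|---|
| Synopsis, sample size | one 8-week series; centres already trained |
| Hospital inclusion criteria | one consecutive 8-week window per site |
| Training platform | training intended before the audit starts |
| Primary objective | one rate, no contrast |
| Statistical analysis plan | at least two periods; the second is exposed |
| Planned additional analyses | a post-implementation phase; change per hospital |

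The two phases under Data collection and follow-up do not supply the missing period. They are the index admission and the 30-day follow-up of the same patients. No section names EAGLE 1 data as the first period, and centres that did not take part in EAGLE 1 would have none. The reference list includes papers on dog-leg, stepped-wedge and repeated-cross-section cluster designs. The two-period wording would fit those designs.

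**2. Can the terms be estimated?**

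Take the fixed-effect design matrix with columns for intercept, one risk factor (such as ASA grade), period and exposure. All four coefficients are estimable only if the rank is 4.

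- One period, all patients exposed by the period rule: period and exposure are constant and collinear with the intercept. Rank 2 of 4.
- Two periods, no hospital exposed in the first and all exposed in the second: the period and exposure columns are identical. Rank 3 of 4, so training and time cannot be separated.
- Two periods with some hospitals still unexposed in the second: rank 4 of 4. The protocol describes no such rollout.

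The model sentence names a time effect but no separate exposure coefficient. If period is the only such term, the one-period matrix has three columns and still rank 2, so the period coefficient is not estimable. With two periods that single coefficient could be fitted, but it would combine training with calendar time.

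**3. Can the data answer the objective without those terms?**

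The protocol gives no total sample size, number of hospitals, ICC, power or effect size, so there is no precision figure to reproduce. Its recruitment average does reproduce: 3,208 / 284 = 11.3 patients per centre.

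Inputs: p = 8.1% (Existing international data) and m = 10 patients per hospital (Projected recruitment). The number of hospitals k and the ICC are assumed; 284 is the centre count of the 2015 audit.

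Design effect DE = 1 + (m − 1) × ICC. At ICC 0.05, DE = 1 + 9 × 0.05 = 1.45.

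Half-width = 1.96 × √[p(1 − p) × DE / (k × m)].

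Example, k = 100 and ICC 0.05: 1.96 × √[0.081 × 0.919 × 1.45 / 1000] = 0.0204, or 2.0 percentage points.

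| Hospitals (assumed) | Patients | ICC 0 | ICC 0.05 |
|---|---|---|---|
| 50 | 500 | 2.4 points | 2.9 points |
| 100 | 1,000 | 1.7 points | 2.0 points |
| 284 | 2,840 | 1.0 points | 1.2 points |

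The figure of 10 counts right colectomies, and those without an anastomosis leave the primary denominator. The half-widths are therefore slightly optimistic. A single leak rate can be estimated from one period with no exposure or time term.

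**The case against.** **The model survives if the time term is dropped.** This stands. Without the redundant term the mixed model is estimable, and a crude proportion with a clustered interval is available too. A reader might infer that the audit cannot answer its objective; the documents do not support that. What remains is that the protocol does not state this analysis, so adopting it changes the primary analysis.

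**Exposure is not constant, because uptake varies.** This stands in part. The Training platform section states only an intention, the hospital criteria do not list training, the planned subgroups include centres with under 50% of surgeons trained, and the case report form records whether the senior surgeon completed the module. It would be too strong to say that every centre is fully trained. Only the exposure defined by period is constant. Comparison by uptake is possible, but it is planned as an exploratory subgroup and is not the primary model.

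**EAGLE 1, or early against late entrants, could serve as the two periods.** The protocol says neither. Data from EAGLE 1 would leave training confounded with time. Early against late entry is listed only as an exploratory subgroup; used as the two periods, it would count patients in early, trained centres as unexposed. That would be a misuse, but the protocol does not plan it.

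**The model would understate the rate.** A reader might infer this because the intercept of a random-intercept logistic model describes a median hospital. For a true average of 8.1%, that rate would be 7.8% to 6.0% at assumed logit SDs of 0.3 to 0.9, which is 3% to 26% lower in relative terms. The documents do not support treating this as a defect. They nowhere plan to report the intercept as the leak rate, they define the outcome as a simple proportion, and the planned model contains risk factors, so this covariate-free calculation does not describe it.

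**Validation of the trial is not the primary objective.** This is fair. The word appears in the synopsis background, whereas the primary objective is descriptive. An external comparison is therefore optional.

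**Conclusion.** The point holds. The primary analysis depends on a second period that the protocol does not define and that conflicts with its single 8-week design. The period effect and the period-defined exposure cannot be estimated (rank 2 of 4). The post-implementation wording and the reverse analysis of change share the fault, since change per hospital needs a before measurement.

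This conclusion rests on the design as written, one window per site with no comparator period, and on no numerical assumption. Only the precision figures use assumed hospital numbers and ICCs. No bias of a given size follows from the documents. The defect is a primary analysis that cannot be run as stated and that leaves the required rate and its interval unspecified. It should be corrected before analysis, because a repair chosen after the data are seen would be post hoc.

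**What to change.** 1. In the Statistical analysis plan section, delete the second-period exposure rule, the intention-to-treat wording and the fixed time effect.
2. In Planned additional analyses, delete the reverse analysis of change and reword the post-implementation phrase so that uptake refers to training completed before the audit window.
3. State the primary analysis as the 30-day leak proportion among patients with a primary anastomosis over the 8-week window, with a 95% confidence interval that allows for hospital clustering. A risk-adjusted mixed model without the period term can be supportive.
4. If the aim of validating the earlier trial is kept, choose one of two courses. Either name one comparator, such as pre-training EAGLE 1 data from returning centres or the planned comparison by training uptake, and label it non-randomised; or limit the conclusion to a descriptive rate.

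The cost is protocol wording and modest analysis work, with no new patients or visits. The price in interpretation is that no before/after effect of training can be claimed from this audit alone.
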